## APPENDIX C: CLL/SLL RESPONSE CRITERIA

Treatment response will be determined per the investigators' assessment, according to Hallek et al.

Group	Parameter	CR	PR	PD	SD
A	Lymph nodes	None $\geq 1.5$ cm	Decrease $\geq 50\%$ (from baseline)*	Increase $\geq 50\%$ from baseline or Change of $-49\%$ to $+49\%$ from response	
	Liver and/or spleen size†	Spleen size $< 13$ cm; liver size normal	Decrease $\geq 50\%$ (from baseline)	Increase $\geq 50\%$ from baseline or Change of $-49\%$ to $+49\%$ from response	
	Constitutional symptoms	None	Any	Any	Any
	Circulating lymphocyte count	Normal	Decrease $\geq 50\%$ from baseline	Increase $\geq 50\%$ over baseline	Change of $-49\%$ to $+49\%$
B	Platelet count	$\geq 100 \times 10^9/L$	$\geq 100 \times 10^9/L$ or increase $\geq 50\%$ over baseline	Decrease of $\geq 50\%$ from baseline secondary to CLL	Change of $-49$ to $+49\%$
	Hemoglobin	$\geq 11.0$ g/dL (untransfused and without erythropoietin)	$\geq 11$ g/dL or increase $\geq 50\%$ over baseline	Decrease of $\geq 2$ g/dL from baseline secondary to CLL	Increase $< 11.0$ g/dL or $< 50\%$ over baseline, or decrease $< 2$ g/dL
	Marrow	Normocellular, no CLL cells, no B-lymphoid nodules	Presence of CLL cells, or of B-lymphoid nodules, or not done	Increase of CLL cells by $\geq 50\%$ on successive biopsies	No change in marrow infiltrate

\*Sum of the products of 6 or fewer lymph nodes (as evaluated by CT scans and physical examination in clinical trials or by physical examination in general practice).

†Spleen size is considered normal if  $< 13$  cm. There is not firmly established international consensus of the size of a normal liver; therefore, liver size should be evaluated by imaging and manual palpation in clinical trials and be recorded according to the definition used in a study protocol.

CR, complete remission (all of the criteria have to be met);  
 PR, partial remission (for a PR, at least 2 of the parameters of group A and 1 parameter of group B need to improve if previously abnormal; if only 1 parameter of both groups A and B is abnormal before therapy, only 1 needs to improve);  
 PD, progressive disease (at least 1 of the criteria of group A or group B has to be met);  
 SD, stable disease (all of the criteria have to be met; constitutional symptoms alone do not define PD).

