#### **Abbreviated Eligibility Criteria**

##### Main Inclusion Criteria

- Men and women, aged >18 years
- "Warm" or "cold" AIHA in patients with CLL, relapsed/refractory (RR) after first line treatment with oral prednisone (with or without rituximab), defined by:
  - anemia (Hgb≤10 g/dL; or Hgb>10 g/dL dependent on transfusions to maintain this level of hemoglobin), and
  - laboratory evidence of hemolysis: 3 of 4 markers present (increased reticulocyte count, increased indirect bilirubin, increased lactate dehydrogenase, haptoglobin < institutional lower limit of normal)
- Positive DAT (score ≥ 1+) – either IgG DAT, C3 DAT, or both. Eligibility of patients with Coombs-negative AIHA should be confirmed by the trial investigator at each respective study site.
- ECOG performance status grade ≤2
- Histologically or flow cytometry confirmed diagnosis of CLL/SLL
- Prior to starting study agent, participant must have organ function as defined below:
  - Direct bilirubin ≤3 X institutional upper limit of normal (ULN) or 1 mg/dL, whichever is higher, if deemed related to hemolysis by the investigator
  - AST or ALT ≤3 X institutional ULN
  - Estimated CrCl using the Cockcroft-Gault equation (or an alternative equation, per institutional standard) ≥30 mL/min.
  - Absolute neutrophil count (ANC) ≥500/mm^3, platelet count ≥30,000/mm^3.
  - PT/INR or aPTT <2 x ULN. Exception: subjects receiving warfarin are excluded; however, those receiving other anticoagulant therapy who have a higher INR/aPTT are permitted to enroll

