##### Nature of Illness and Illness Related Criteria

\_\_\_4. "Warm" or "cold" AIHA in patients with CLL, relapsed/refractory (RR) after first line treatment with oral prednisone (with or without rituximab), defined as:

- anemia ( $Hgb \leq 10$  g/dL; or  $Hgb > 10$  g/dL dependent on transfusions or maintenance therapy (rituximab, cyclosporin, etc) to maintain this level of hemoglobin, and
- laboratory evidence of hemolysis – presence of 3 of 4 markers (increased reticulocyte count, increased indirect bilirubin, increased lactate dehydrogenase, absent haptoglobin)

\_\_\_5. Positive DAT (score  $\geq 1+$ ) – either IgG DAT, C3 DAT, or both. Eligibility of patients with Coombs-negative AIHA should be confirmed by the trial investigator at each respective study site.

\_\_\_6. Histologically or flow cytometry confirmed diagnosis of CLL/SLL

\_\_\_7. Participant must be able to swallow tablets or capsules.

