*Toxicity:* incidence, type, severity, and attribution of toxicities on the study will be assessed by CTCAE v5.0 (non-hematologic) and IWCLL 2018 (hematologic). All patients who receive at least 1 dose of acalabrutinib will be included in the toxicity analysis.

*CLL ORR after 6 or 12 cycles:* it will be defined as the proportion of patients achieving CLL CR /PR after 6 or 12 cycles respectively. Patients evaluable for this endpoint include: 1) those who receive at least 6 or 12 cycles of acalabrutinib and have a CLL response evaluation at those timepoints; 2) patients who terminate acalabrutinib treatment prior to completing 6 or 12 cycles due to CLL progressive disease (they will be counted as non-responders).

*CLL-specific Event-free Survival (EFS):* it will be defined as the time from start of acalabrutinib treatment until death, time of CLL progression, or start of new therapy for CLL, whichever earlier. Patients without death, CLL recurrence/progression, or start of new therapy for CLL will be censored at the last follow-up.

*Duration of CLL-response:* it will be estimated among patients who achieve CLL CR/PR on protocol treatment. It will be defined as the time from the first documented CLL CR/PR until death, time of CLL recurrence/progression, or start of new therapy for CLL, whichever earlier. Patients without death, CLL recurrence/progression, or start of new therapy for CLL will be censored at the last follow-up.

*AIHA sustained response:* it will be estimated among patients who achieve AIHA CR/PR on protocol treatment. It will be defined as the time from the first documented AIHA CR/PR until death or relapse of AIHA, whichever is earlier. Patients without death or AIHA relapse will be censored at the last follow-up or when they begin new therapy for AIHA or CLL.

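### CLL response can be scored on hemoglobin recovery from AIHA alone in participants with no abnormal group A parameter at baseline, and the CLL-evaluable set does not exclude them

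*Combined protocol and SAP*

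**What the plan says.** **Entry.** The CLL criterion (Section 3.1, item 6) is "Histologically or flow cytometry confirmed diagnosis of CLL/SLL". Nothing in Sections 3.1 or 3.2 asks for active, measurable or treatment-requiring CLL. For AIHA, the synopsis admits "anemia (Hgb≤10 g/dL; or Hgb>10 g/dL dependent on transfusions to maintain this level of hemoglobin"; Section 3.1, item 4 widens the higher-hemoglobin route to patients "dependent on transfusions or maintenance therapy (rituximab, cyclosporin, etc) to maintain this level of hemoglobin". Laboratory evidence of hemolysis is also required.

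**CLL response.** Appendix C puts nodes, liver/spleen, constitutional symptoms and lymphocyte count in group A, and platelets, hemoglobin and marrow in group B. For PR, hemoglobin must reach 11 g/dL or rise by half. For CR it must be at least 11 g/dL, untransfused and without erythropoietin; the PR cell has no transfusion condition. For PD, the fall must be at least 2 "g/dL from baseline secondary to CLL". The PR and CR cells carry no such cause. The PR rule is that "at least 2 of the parameters of group A and 1 parameter of group B need to improve if previously abnormal", followed by the exception "if only 1 parameter of both groups A and B is abnormal before therapy, only 1 needs to improve".

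**Who counts.** Section 11.2 makes evaluable for CLL ORR "those who receive at least 6 or 12 cycles of acalabrutinib and have a CLL response evaluation at those timepoints", plus those who stop early for CLL progression, who count as non-responders. Baseline CLL burden plays no part. Duration of CLL response runs from the first CR or PR.

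**The concern.** The trial enrolls people because they are anemic from hemolysis, then uses hemoglobin as one of the measures of CLL response without asking why it changed. In a participant with little or no measurable CLL, a hemoglobin rise may be the only improvement available, and it is the quantity that the AIHA endpoint already measures.

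At stake is the secondary objective on efficacy in CLL: CLL ORR after 6 and 12 cycles, and duration of CLL response. For duration the asymmetry matters twice. An AIHA-driven rise can start the clock, but an AIHA-driven fall is not CLL progression and does not stop it.

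**Working it through.** **Plan figures.** The plan gives no sample size, power or expected rate for CLL ORR, so there is no figure to reproduce for this endpoint. For context, the primary design reproduces: with 10 or more responders of 20, the exact binomial probability is 0.048 at a true rate of 0.30 and 0.872 at 0.60, against the stated 0.048 and approximately 87%.

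**Step 1: apply the PR rule when only hemoglobin improves.** Count the group A parameters with a PR threshold (nodes, liver/spleen, lymphocytes). Constitutional symptoms are left out because any state satisfies their PR cell. The exception can be read as one abnormal parameter in total, or as one in each group.

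| Abnormal group A | Abnormal group B | One in total | One per group |
|---|---|---|---|
| 0 | hemoglobin only | PR | PR |
| 0 | hemoglobin and others | PR | PR |
| 1 | hemoglobin only | not PR | PR |
| 1 | hemoglobin and others | not PR | not PR |
| 2 or 3 | hemoglobin, with or without others | not PR | not PR |

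Row 1 follows from the exception. Row 2 follows from the main rule, because no group A parameter was previously abnormal and one group B parameter has improved. In row 3 the two readings disagree. Row 4 can apply through marrow, a group B parameter: the Study Calendar (Section 10.0, footnote v) makes screening marrow optional, so its baseline status may be unknown.

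**Step 2: compare the hemoglobin thresholds.** For baseline b in g/dL, the Appendix C PR minimum is min(11, 1.5b), and the Appendix B AIHA PR minimum on either route is min(10, b+2).

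- b = 6: Appendix C min(11, 9) = 9; Appendix B min(10, 8) = 8.
- b = 8: Appendix C min(11, 12) = 11; Appendix B min(10, 10) = 10.
- b = 10: Appendix C min(11, 15) = 11; Appendix B min(10, 12) = 10.

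An AIHA CR needs more than 12 g/dL, so it always clears the Appendix C hemoglobin PR level. An AIHA PR clears it only sometimes.

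**Step 3: the opposite direction.** CLL CR needs every criterion, so hemoglobin held below 11 g/dL by AIHA rules it out whatever the CLL has done. For PR, take a participant whose nodes and spleen both shrink by at least half, with hemoglobin as the only abnormal group B parameter. If hemoglobin neither reaches 11 g/dL nor rises by half, the group B condition is unmet. If abnormal platelets improve, it is met.

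**Step 4: size.** One participant is 1/20 = 5 percentage points. For scale, let f be the share of participants with hemoglobin as the only abnormal parameter, and r the share of those who reach the Appendix C level. The addition to CLL ORR is 100 × f × r points. Neither f nor r is in the documents. For r, the design's 0.30 and 0.60 are borrowed, although those are AIHA response rates and not rates of passing Appendix C.

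| f (assumed) | r = 0.30 | r = 0.60 |
|---|---|---|
| 0.05 | 1.5 points | 3 points |
| 0.10 | 3 | 6 |
| 0.20 | 6 | 12 |
| 0.30 | 9 | 18 |

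At n=20 this is 0.3 to 3.6 participants.

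**The case against.** The strongest defense is that the endpoint follows a published standard by investigator assessment (Sections 11.2 and 11.2.1), and that applying it unmodified keeps CLL ORR comparable with other trials. Appendix C is a summary table, and whether the full guideline deals with autoimmune cytopenia cannot be checked from these documents. This stands as a reason to keep the standard as the main definition. It does not close the gap, because nothing in the plan tells the investigator to set AIHA-related hemoglobin aside.

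Several stronger readings are tempting and are not supported:

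- **That AIHA recovery generally scores as CLL response.** It cannot do so alone with two or more abnormal group A parameters. A rise from 8 to 10 g/dL is an AIHA PR but fails the Appendix C hemoglobin level. Some entrants on transfusion or maintenance therapy may already be at or above 11 g/dL.
- **That a participant with lymphocytosis only is certain to be misclassified.** That needs the one-per-group reading and no other abnormal group B parameter.
- **That persistent AIHA systematically lowers CLL ORR.** The PR effect is conditional, and the marrow PR cell accepts a marrow that was not done, so failure of group B is arguable. AIHA relapse is a reason to stop therapy (Section 5.6), but only early stopping for CLL progression counts as non-response. Those who stop early for AIHA relapse can leave the denominator instead of lowering the rate.
- **That CLL ORR cannot be read as a CLL result.** It is a secondary rate reported with a 95% confidence interval and no test (Section 12.4.2). At 10/20 the exact interval is about 27% to 73%, wide beside a shift of one participant. CLL-specific event-free survival does not use the PR rule.

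**Conclusion.** The point holds in limited form. On the text, a participant with no abnormal group A parameter at baseline can be a CLL PR because hemolysis stopped; with one, this depends on an exception whose meaning the plan must settle; with two or more, it does not happen. In the other direction, AIHA that keeps hemoglobin below 11 g/dL blocks CLL CR, and may block PR when hemoglobin is the only abnormal group B parameter.

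The certain size is 5 points of CLL ORR per misclassified participant at n=20. The 1.5 to 18 points above are an illustration on assumed shares, not an estimate: the documents do not give the expected CLL burden, so the number affected cannot be derived. The primary AIHA endpoint and its design are unaffected. This is a gap in a secondary endpoint worth closing before CLL responses are analyzed.

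**What to change.** 1. In Section 11.2, limit the evaluable set for CLL ORR and duration of CLL response to participants with at least one abnormal group A disease parameter at screening (nodes, liver/spleen or lymphocyte count), and report how many are excluded.
2. Keep the iwCLL criteria as the main definition, including the two-parameter group A rule. Removing hemoglobin from them outright would depart from the stated standard, and asking for just one group A improvement could loosen the PR rule for participants with several abnormal parameters.
3. State in Appendix C whether the single-parameter exception means one abnormal parameter in total or one per group. Item 1 alone does not settle row 3 of the first table.
4. Pre-specify a sensitivity analysis of CLL ORR that leaves out the hemoglobin criterion when baseline anemia is attributed to AIHA, and report it beside the main result.

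The cost is wording, plus a smaller denominator for a secondary endpoint. The baseline set can be defined from the screening CT, examination and blood count already in the Study Calendar. The AIHA attribution in item 4 is an investigator judgement in an open-label trial, which is a reason to keep it to the sensitivity analysis.

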Acalabrutinib has received FDA approval in therapy of CLL based on two large randomized trials, ASCEND and ELEVATE TN, in patients with R/R and TN CLL, respectively, which were conducted after encouraging results of the phase I/II ACE-CL-001 trial (NCT02029443) evaluating the safety and efficacy of acalabrutinib for patients with relapsed CLL. A total of 61 patients that had received a median of 3 previous therapies were enrolled and assigned to receive oral acalabrutinib dose of 100, 175, 250 or 400 mg once daily in the phase I dose-escalation portion, or 100 mg (bid) in the phase II portion of the study. The authors reported an ORR of 95% (57 of 60 evaluable patients). Notably, ORR was 100% (n = 18) in patients with chromosome 17p13.1 deletion. Additional sub-analyses of patient subgroups from the ACE-CL-001 trial have reported that among study participants that were intolerant to treatment with ibrutinib (i.e., experienced ibrutinib-related AEs), the ORR was 76% (22 of 29 evaluable patients), including 1 complete, 14 partial and 7 partial responses with lymphocytosis. A median time of 3.7 months to at least partial response was observed. Additionally, in a sub-group of patients with Richter Transformation (n = 29), the ORR was 38%, with the median duration of response reported as 5.7 months.

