### 6.1 Acalabrutinib

Per the Investigator Brochure edition 9.0 dated Feb 2020 the expected toxicities for acalabrutinib are:

System Organ Class	Adverse Reactions
Infections and infestations a	
Very common	Infection b , upper respiratory tract infection, lower respiratory tract infection c , urinary tract infection
Common	Herpesvirus infection
Blood and lymphatic system disorders d	
Very common	Neutropenia e , anemia f , thrombocytopenia g , lymphocytosis h
Nervous system disorders	
Very common	Headache, dizziness
Rare	Progressive multifocal leukoencephalopathy
Gastrointestinal system disorders	
Very common	Diarrhea, nausea
Musculoskeletal and connective tissue disorders	
Very common	Musculoskeletal pain i , arthralgia
Metabolism and nutrition disorders	
Rare	Tumor lysis syndrome
General disorders and administration site conditions	
Very common	Fatigue j
Skin and subcutaneous tissue disorders	
Very common	Bruising k , rash l
Vascular disorders	
Very common	Hemorrhage m
Cardiac disorders	
Common	Atrial fibrillation or flutter, hypertension
Laboratory abnormality	
Very common	Uric acid increase, ALT increase, AST increase, bilirubin increase
Neoplasms, benign, malignant, and unspecified	

System Organ Class	Adverse Reactions
Common	Second primary malignancy, non-melanoma skin cancer
a. Includes any adverse reactions involving infection or febrile neutropenia	
b. Upper respiratory tract infection, nasopharyngitis and sinusitis	
c. Includes pneumonia, lower respiratory tract infection, bronchitis, bronchiolitis, tracheitis, and lung infection	
d. Derived from adverse reaction and laboratory data	
e. Includes neutropenia, neutrophil count decreased, and related laboratory data	
f. Includes anemia, red blood cell count decreased, and related laboratory data	
g. Includes thrombocytopenia, platelet count decreased, and related laboratory data	
h. Includes lymphocytosis, lymphocyte count increased, and related laboratory data	
i. Includes back pain, bone pain, musculoskeletal chest pain, musculoskeletal pain, musculoskeletal discomfort, myalgia, neck pain, pain in extremity and spinal pain	
j. Includes asthenia, fatigue, and lethargy	
k. Includes bruise, contusion, and ecchymosis	
l. Includes rash, dermatitis, and other related terms	

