m. Includes hemorrhage, hematoma, hemoptysis, hematuria, menorrhagia, hemarthrosis, and epistaxis	

Very common ( $\geq 1/10$ ); Common ( $\geq 1/100$  to  $< 1/10$ ); Uncommon ( $\geq 1/1,000$  to  $< 1/100$ ); Rare ( $\geq 1/10,000$  to  $< 1/1,000$ ); Very rare ( $< 1/10,000$ ); not known (cannot be estimated from the available data).

The important risks of acalabrutinib are the following:

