
- n. Adverse events will be assessed using the [CTCAE v5.0](#) (non-hematologic) and IWCLL 2018 (hematologic). SAEs related to study procedures will be recorded and reported from the time the participant signs the Consent Form. Please see Section 14 for routine AE assessing and reporting ([Section 14.6](#)) and SAE reporting ([Section 14.7](#)).
- o. Electrocardiogram (ECG): resting 12-lead ECGs will be recorded at screening, and as clinically indicated throughout the study.
- p. A serum or urine pregnancy test is required during screening for women of childbearing potential. If urine pregnancy results cannot be confirmed as negative, a serum pregnancy test is required. For Day 1 Cycle 1, a pregnancy test may be omitted if previously obtained within 72 hours prior to first dose of trial treatment. Pregnancy tests (serum and/or urine tests) should be repeated, if required, per institutional guidelines. A serum or urine pregnancy test will be done for women of childbearing potential any time for missed or late menses, and at the end of treatment. If the urine pregnancy test is positive, a serum pregnancy test must be performed per institutional standards.
- q. Hematology: Hemoglobin; hematocrit; mean corpuscular volume (MCV); reticulocyte count (absolute and relative); leukocyte count; differential count; platelets. Additional hematology may be performed thereafter as clinically indicated
- r. Biochemistry: Comprehensive metabolic panel (CMP), including: Na, K, Cl, CO2, BUN, Creatinine, Ca, glucose, Albumin, Alkaline Phosphatase, total bilirubin, AST, ALT, total protein.
- s. Serum immunoglobulins, IgG, IgM, and IgA are required at screening and on cycle 13 D1.
- t. Hemolysis parameters: Reticulocytes, lactate dehydrogenase (LDH), bilirubin (direct/indirect), haptoglobin and DAT.
- u. Computed tomography (CT) scan of neck, chest, abdomen and pelvis per institutional guidelines (with intravenous contrast, wherever possible) will be performed for response assessment at screening, C7D1, C13D1 and annually thereafter. CLL response will be evaluated every time imaging is performed. A bone marrow biopsy will be performed only if CR is suspected. Positron emission tomography with CT (PET-CT) and/or magnetic resonance imaging studies may be performed as clinically indicated, per institutional guidelines, and is acceptable in place of CT, if performed.

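### As printed, Appendix C makes an isolated lymphocyte rise of 50% or more sufficient for CLL progression, with no exemption on treatment, although lymphocytosis is a very common acalabrutinib reaction

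*Combined protocol and SAP*

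**What the plan says.** Appendix C tabulates CLL response by parameter. Circulating lymphocyte count is in group A, and its PD cell reads "Increase $\geq 50\%$ over baseline". The note below the table gives the combination rule: "PD, progressive disease (at least 1 of the criteria of group A or group B has to be met". The platelet and hemoglobin PD cells carry a cause limit, "from baseline secondary to CLL"; the lymphocyte cell carries none. The only exemption printed is for constitutional symptoms on their own. For PR, "at least 2 of the parameters of group A and 1 parameter of group B need to improve if previously abnormal", with a lighter requirement for patients who have few abnormal parameters at the start. Appendix C and Section 11.2.1 leave the call to the investigator, following the cited iwCLL guideline.

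Section 6.1 puts lymphocytosis among the very common blood disorders. Its footnote reads "h. Includes lymphocytosis, lymphocyte count increased, and related laboratory data", and the frequency key reads "Very common ( $\geq 1/10", that is, at least 1 in 10. Section 2.2.1 reports an acalabrutinib ORR of 76% in ibrutinib-intolerant patients, "including 1 complete, 14 partial and 7 partial responses with lymphocytosis".

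On timing, Section 10.0 (footnote u) says that CT "will be performed for response assessment at screening, C7D1, C13D1 and annually thereafter", and CLL response is judged at each scan. Treatment may run to 36 cycles (Sections 2.4 and 5.3).

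**The concern.** The printed rule cannot tell a lymphocyte rise caused by the drug from one caused by the disease, and the plan itself expects the first kind to be very common. The table limits the two group B blood counts to changes caused by CLL but does not do so for the count that this drug is listed as raising. It also lacks a response category that the plan's own background counts as response.

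Two things are at stake. One is the meaning of the secondary CLL endpoints: a patient whose nodes and spleen are shrinking could be reported as progressing. The other is treatment, because CLL progression is a removal criterion in Section 5.6. A patient could lose a drug that is controlling the hemolysis.

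**Working it through.** **1. The plan's own figure.** From Section 2.2.1: 1 + 14 + 7 = 22 responders, and 22/29 = 75.9%, which matches the stated 76%. Without the 7 partial responses with lymphocytosis it would be 15/29 = 51.7%, a gap of 7/29 = 24.1 points. So the handling of this category can matter. It is not a forecast for this trial: the subgroup is different, and the plan does not say how many of the 7 had a rise of 50% or more.

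**2. PD cells side by side (Appendix C).**
- Lymphocytes (group A): up 50% or more over baseline; no cause limit.
- Platelets (group B): down 50% or more; must be due to CLL.
- Hemoglobin (group B): down 2 g/dL or more; must be due to CLL.

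One criterion suffices, so the lymphocyte row alone gives PD.

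**3. PR and PD at one visit.** Take a patient with nodes down 50%, spleen down 50%, hemoglobin up from below 11 g/dL to 11 g/dL or more, and lymphocytes up 50%. Nodes and spleen supply two group A improvements and hemoglobin one group B improvement, so PR is met. The lymphocyte row meets PD. No precedence rule is printed.

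**4. Route to each endpoint.**
- CLL ORR at 6 and 12 cycles: direct, if the scan at C7D1 or C13D1 is scored PD.
- CLL EFS: direct, at any on-treatment scan, since progression is an event (Section 11.2).
- Removal: direct, under Section 5.6.
- Duration of CLL response: indirect. It needs a documented CR or PR first and a qualifying rise over baseline later.
- AIHA ORR at 12 cycles: indirect. It needs PD at C7D1, removal before 12 cycles, and a patient who would otherwise have been an AIHA responder. Section 11.2 then counts that patient as a non-responder.

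**5. Size per patient.** The documents give no rate of rises of 50% or more at the scored visits, so only the effect of one rescored responder, 1/n, can be computed. For an assumed 22, 20 or 15 evaluable patients: 1/22 = 4.5, 1/20 = 5.0 and 1/15 = 6.7 points. With an assumed starting count of 16/20 and exact (Clopper-Pearson) 95% intervals:
- 16/20 = 80% (56.3% to 94.3%)
- one rescored: 15/20 = 75% (50.9% to 91.3%)
- two rescored: 14/20 = 70% (45.7% to 88.1%)

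**The case against.** The strongest reply is that the table is not the whole criterion. Appendix C and Section 11.2.1 follow the cited iwCLL guideline, and Section 11.2 defines CLL ORR by standard iwCLL criteria. If that guideline exempts drug-related lymphocytosis, investigators may never apply the printed cell. The guideline is not part of the documents, so this can be neither confirmed nor excluded. What stands is that the effect depends on how investigators use the appendix. The need for the edit remains: if the guideline has an exemption, the printed table conflicts with it; if not, the gap is substantive.

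It is also fair that a patient who meets both PR and PD is an ambiguous case, not a certain PD. The figures per patient therefore apply only when PD is chosen.

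Two stronger readings are tempting and are not supported:
- *At least two of 22 patients will be rescored, since 22 × 0.1 = 2.2.* The very common band covers lymphocytosis and related laboratory findings without limit on size or time. It does not give the share with a rise of 50% or more at C7D1 or C13D1, and a rise that resolves before C7D1 may never be formally scored.
- *The primary endpoint is compromised, because Section 11.1 counts stopping for CLL progression before 6 cycles as non-response.* The first scheduled on-treatment CLL assessment is C7D1, and Section 11.2.1 ties assessments to CT. Hematology is drawn every cycle and Section 5.6 does not tie PD to a scan, so an earlier call is conceivable. Nothing in the documents gives it a frequency, and no loss of power can be claimed.

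**Conclusion.** The concern holds for the criteria as printed. Following Appendix C literally can record an expected drug effect as CLL non-response or a CLL EFS event at C7D1, C13D1 or an annual on-treatment scan, and can end protocol therapy. The overlap of PR and PD is a second defect in the same table and lets two sites score the same patient in opposite ways.

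The reach is limited. The CLL endpoints are secondary and reported as estimates with intervals. Duration of CLL response and 12-cycle AIHA ORR are exposed only through further steps, and the primary endpoint is not claimed to be affected. The size cannot be derived from the documents; each rescored responder costs 1/n of CLL ORR, which is 4.5 to 6.7 points under the assumed 15 to 22 evaluable patients. The conclusion assumes that at least some investigators apply the printed table and not an exemption from outside it.

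**What to change.** Change the wording of Appendix C, with a cross-reference in Sections 5.6 and 11.2:

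1. An isolated lymphocyte rise on treatment, with no other group A or B PD criterion met, is not PD. The patient is classified on the remaining rows. This also settles the overlap of PR and PD.
2. Add a category of PR with lymphocytosis, tabulate it separately, and report CLL ORR with and without it.
3. Limit the exemption. A count that has normalised or met the PR threshold and then rises again by 50% or more is reviewed as possible progression. Without this limit, the exemption could cover a true relapse in the count for up to 36 cycles.
4. After permanent stop of acalabrutinib, if the count is still raised at that point, judge the lymphocyte PD criterion against the count at drug stop and not the pre-treatment baseline. Otherwise a persisting drug-related count becomes PD at the next off-treatment assessment, while EFS and duration of response run up to 12 months after the last dose.

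No new data are needed: CT is scheduled, and hematology with differential is collected through treatment, at end of treatment and in follow-up. The cost is one more response category, and some progression that shows only in the count is recorded later than under the printed rule.
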